# **AMENDMENT 1 (11-MAR-2015)**

#### Amendment rationale

The purpose of this amendment is as follows:

- Inclusion/Exclusion criteria were modified to clarify patient eligibility and align with standard of care treatment practice for cholangiocarcinoma.
- Hyperphosphatemia management guidelines were updated to provide more detail regarding the prophylaxis of hyperphosphatemia and how to modify BGJ398 dose administration in response to elevated serum phosphorous levels.
- Serum creatinine and creatinine clearance exclusion criteria were revised to align
  with current medical practice and provide consistency across BGJ398 protocols.
  BGJ398 has not been demonstrated to be nephrotoxic.
- Evaluations of cardiac function by echocardiogram/MUGA scan were added on day 1 of cycles 2, 3 and 4 to monitor changes in left ventricular ejection fraction (LVEF) and make monitoring frequency consistent across BGJ398 protocols. Asymptomatic and reversible decreases in LVEF have been noted in patients treated with BGJ398.
- The emergence of acquired resistance to therapy is a major problem for patients with cancer. Under this amendment, language has been inserted to allow the collection of tumor tissue at baseline and upon the development of acquired resistance to treatment as described in the optional companion sample collection protocol. The purpose of these samples and a sample of normal tissue to aid in the identification of somatic variants in the tumor is to identify genetic changes in the tumor that may underlie treatment resistance. Two blood samples are also collected to test the potential value of circulating cell free tumor DNA as a possible replacement in some circumstances for tumor biopsies.
- Minor inconsistencies, edits, and typographical errors that were identified after the finalization of the original protocol have been corrected with this amendment.

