  - Continuous or intermittent small molecule therapeutics within a period of time that is  $\leq 5$  t1/2 or  $\leq 4$  weeks (whichever is shorter) prior to starting study drug
  - Any other investigational agents within a period of time that is  $\leq 5$  t1/2 or less than the cycle length used for that treatment or  $\leq 4$  weeks (whichever is shortest) prior to starting study drug
  - Wide field radiotherapy (including therapeutic radioisotopes such as strontium 89) ≤ 4 weeks or limited field radiation for palliation ≤ 2 weeks prior to starting study drug
- 10. Patients who are currently receiving, or are planning to receive during participation in this study, treatment with agents that are known strong inducers or inhibitors of CYP3A4 and medications which increase serum phosphorus and/or calcium concentration are excluded. (Refer to Appendix 2 for list of prohibited medications). Patients are not permitted to receive enzyme-inducing anti-epileptic drugs
- 11. Consumption of grapefruit, grapefruit juice, grapefruit hybrids, pomegranates, star fruits, pomelos, Seville oranges, or products containing juice of these fruits, within 7 days prior to first dose
- 12. Insufficient bone marrow function
  - ANC  $< 1,000/\text{mm}^3 [1.0 \times 10^9/\text{L}]$
  - Platelets  $< 75,000/\text{mm}^3 [75 \times 10^9/\text{L}]$
  - Hemoglobin < 9.0 g/dL
- 13. Insufficient hepatic and renal function

- Total bilirubin > 1.5x ULN (for patients with documented Gilbert syndrome, direct bilirubin ≤1.5x ULN and enrollment requires approval by the medical monitor)
- AST/SGOT and ALT/SGPT > 2.5x ULN (AST and ALT > 5x ULN in the presence of liver metastases)
- Serum creatinine > 1.5x ULN and a calculated (using the Cockcroft-Gault formula [Cockcroft 1976]) or measured creatinine clearance of < 45 mL/min
- 14. Abnormal calcium or phosphorus:
  - Inorganic phosphorus outside of normal limits
  - Total serum calcium (can be corrected) outside of normal limits
  - Calcium-phosphorus product ≥55 mg²/dL²
- 15. Clinically significant cardiac disease including any of the following:
  - Congestive heart failure requiring treatment (NYHA Grade ≥ 2), LVEF < 50% as determined by MUGA scan or ECHO, or uncontrolled hypertension (refer to WHOISH guidelines)
  - History or presence of clinically significant ventricular arrhythmias, atrial fibrillation, resting bradycardia, or conduction abnormality

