## 6.2 Dose modifications

# 6.2.1 Dose modifications and dose delay

For patients who do not tolerate the protocol-specified dosing schedule, dose adjustments are permitted in order to allow the patient to continue the study treatment. All dose modifications should be based on the worst preceding toxicity (Table 5, Table 6). Dosage changes must be recorded on the Dosage Administration Record CRF.

The following guidelines should be applied.

Each patient will be allowed 3 dose reductions according protocol-specified dose modifications for AEs. A QED medical monitor or designee approval is required for the third dose reduction (Table 4).

Following resolution of toxicity to baseline or  $\leq$  Grade 1, treatment is resumed at either the same or lower dose of study drug as per the criteria in Table 5. If treatment is

resumed at the same dose of study drug, and the same toxicity recurs with the same or worse severity regardless of duration, dose must be reduced to the next lower dose level. If treatment is resumed at the lower dose of study drug, and the same toxicity recurs with the same or worse severity, the patient should have a second dose reduction.

Patients who discontinue study treatment for a study related adverse event or an abnormal laboratory value must be followed as described in Section 6.2.2.

Study drug must be permanently discontinued for a delay of >14 days and may only be restarted with written permission of a QED Therapeutics' medical monitor if (1) the delay was not due to an AE that requires permanent study drug discontinuation as provided in Table 5, and (2) the patient has not met other criteria requiring study drug discontinuation in Section 7.1.4, and it is the Investigator's opinion that no safety concerns are present.

Table 4: Dose reduction table

Dose reduction				
	Starting dose level 0	Dose level -1	Dose level -2	Dose level -3
BGJ398	125 mg	100 mg	75 mg	50 mg a

Dose reduction to 50 mg requires QED Therapeutics medical monitor approval. Details are provided in the text above.

 Table 5:
 Criteria for interruption and re-initiation of BGJ398 treatment

Worst Toxicity CTCAE v4.03 Grade (unless otherwise specified)	Dose Modifications any time during a cycle of therapy
Cardiac disorders	
Cardiac - Prolonged QTcF interval	

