Grade 3 (platelet $<$ 50 - 25 x 10 $^9$ /L ) with Grade $\ge$ 2 bleeding or Grade 4 (platelet $<$ 25 x 10 $^9$ /L )	Hold dose of BGJ398 until resolved to CTCAE Grade ≤ 1 or baseline, then ↓ 1 dose level.  If not resolved within ≤14 days, discontinue patient from study treatment.
Investigations – Renal	
Serum creatinine	
Creatinine clearance <45 mL/min (calculated or measured)	Hold BGJ398 until creatinine clearance is ≥45 mL/min regardless of grade.
Serum creatinine Grade 2 (≥1.5 - 3.0 x ULN or 1.5-3.0 × baseline)	Hold dose of BGJ398 until resolved to Grade ≤1 or baseline:  If resolved within ≤ 7 days, maintain dose level of BGJ398.  If resolved between > 7 days and 14 days, ↓ 1 dose level of BGJ398.  If not resolved within ≤14 days, discontinue patient from study treatment.
Serum creatinine Grade ≥2	If serum creatinine CTCAE Grade $\geq 2$ has been demonstrated in conjunction with hyperphosphatemia, serum creatinine levels must be repeated at least weekly until resolution. 24-hour urine collection should be obtained as clinically indicated for total phosphate, calcium, protein, and creatinine clearance. Ultrasound examination of the kidneys should be performed as indicated to evaluate $de$ -novo calcifications until resolution or stabilization of creatinine.
Serum creatinine Grade $\geq 3$ (> 3.0 x ULN or >3 × baseline)	Discontinue patient from study treatment.
Investigations – Hepatic	
Blood bilirubin (for patients with Gilbert Syndrome, these dose modifications apply to changes in direct bilirubin only)	
Grade 2 (> 1.5 - 3.0 x ULN)	
 
Hold dose of study drug until resolved to CTCAE Grade ≤ 1
 
If resolved within ≤ 7 days, maintain dose level of BGJ398.
 
If not resolved within ≤ 7 days, ↓ 1 dose level of BGJ398
 

Grade ≥3 (> 3.0 x ULN)	Discontinue patient from study treatment.

Worst Toxicity CTCAE v4.03 Grade (unless otherwise specified)	Dose Modifications any time during a cycle of therapy
	Note: If CTCAE Grade 3 or 4 hyperbilirubinemia is due to hemolysis, then ↓ 1 dose level of BGJ398 and continue treatment at the discretion of the Investigator.
AST or ALT	
Grade 3 (> 5.0 - 20.0 x ULN) without bilirubin elevation > 2.0 x ULN	
 
Hold dose of BGJ398 until resolved to CTCAE Grade ≤ 1 or baseline
 
If resolved within ≤ 7 days, ↓ 1 dose level of BGJ398.
 
If not resolved within ≤ 7 days, discontinue patient from study treatment.
 

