## 10.8 Sample size calculation

#### 10.8.1 Cohort 1

At the time of the first formal interim analysis after amendment 3, the Interim Efficacy Analysis Set 1 will include 72 patients with FGFR2 gene fusions or translocations. The half-width of the exact 95% confidence interval for ORR will not exceed 12%.

With at least 106 patients with FGFR2 gene fusions or translocations, the half-width of the exact 95% confidence interval width of ORR will not exceed 10%.

#### 10.8.2 Cohorts 2 and 3

In Cohorts 2 and 3, patients who are progression-free at the second scheduled scan (approximately 16 weeks from treatment initiation) or later will be considered to be benefiting from study treatment. If the lower bound of the patients who are progression-free at the second scheduled scan (approximately 16 weeks) or later excludes 20%, the treatment will be considered as benefiting the patients.

For Cohort 2, the percentage of patients who are progression-free at the second scheduled scan (approximately 16 weeks) or later will be estimated with 95% exact confidence interval. There will be approximately 20 patients in total. A sample size of 20 will result in the exact 95% confidence interval half width of less than 23%. Patients who withdraw from the study for any reason before the second scheduled scan will be considered as not benefiting from study treatment. Sensitivity analysis will be conducted using the K-M method to estimate PFS >16 weeks.

Table 14 provides some examples of CIs corresponding to observed numbers of patients considered to have benefited from treatment. For example, if 9 of 20 patients are progression-free at the second scheduled scan or later, then the lower bound of the 95% exact confidence interval (CI) will exclude 20%.

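### Exclusion 13 can admit a patient with creatinine clearance below 45 mL/min, for whom Table 5 requires BGJ398 to be held

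*Protocol*

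**What the plan says.** Protocol 5.3 excludes a patient who meets any one listed criterion. The renal limit in exclusion 13 is a single bullet: "Serum creatinine > 1.5x ULN and a calculated (using the Cockcroft-Gault formula", followed by calculated or measured clearance below 45 mL/min. No other listed criterion sets a clearance limit. Exclusion 4 lets the investigator keep out anyone with a medical condition that raises a safety concern.

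In Protocol 6.2.1, Table 5 has a row triggered by clearance below 45 mL/min, with no creatinine condition attached. Its instruction is: "Hold BGJ398 until creatinine clearance is ≥45 mL/min regardless of grade". A separate row, "Serum creatinine Grade 2 (≥1.5 - 3.0 x ULN or 1.5-3.0 × baseline"), also holds drug, but that hold ends at Grade 1 or lower or at the patient's baseline. The text before the table adds that study drug "must be permanently discontinued for a delay of >14 days and may only be restarted with written permission" from the medical monitor, provided certain safety conditions are met.

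The Amendment 1 rationale records that "Serum creatinine and creatinine clearance exclusion criteria were revised to align" with current medical practice and for consistency across BGJ398 protocols, and notes that the drug has not been shown to be nephrotoxic.

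**The concern.** The entry rule needs two abnormal values before it excludes; the dose-hold rule needs only one of them. A patient with stable clearance below 45 mL/min and creatinine at or below 1.5x ULN can be enrolled as the criterion is written, yet already meets a hold condition. Because the clearance row does not release at baseline, that patient resumes only if clearance rises to 45 mL/min. If it does not, the 14-day rule follows.

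At stake is a patient with renal function below the protocol's own dosing floor going through screening, perhaps starting treatment, and then being stopped for a value known at entry. The matter is one of safety and of agreement between two rules.

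**Working it through.** There is no planned figure to reproduce. The check has two parts: what each rule does with each combination of values, and whether the disputed combination can occur.

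**1. The two rules side by side** (Cr = serum creatinine, CrCl = clearance)

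| Cell | Cr | CrCl | Exclusion 13 as written | Table 5 at entry values |
|---|---|---|---|---|
| A | ≤1.5x ULN | ≥45 | eligible | no renal hold (except Cr exactly 1.5x ULN) |
| B | ≤1.5x ULN | <45 | eligible | hold until ≥45, no baseline release |
| C | >1.5x ULN | ≥45 | eligible | creatinine row applies; Grade 2 hold releases at Grade ≤1 or baseline |
| D | >1.5x ULN | <45 | excluded | not applicable |

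Cell B is the conflict. Cell C differs: a patient in the Grade 2 range who enters with a stable raised creatinine can meet the release condition through the baseline clause.

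**2. Can cell B occur?** The protocol names Cockcroft-Gault but does not print it. Assumptions from outside the documents: the standard form, CrCl = (140 − age) × kg × (0.85 if female) / (72 × Cr in mg/dL), and a creatinine ULN of 1.0–1.1 mg/dL for women and 1.2–1.3 mg/dL for men. Ages and weights are illustrative.

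Creatinine at which CrCl equals 45 is (140 − age) × kg × (0.85 if female) / 3240, since 72 × 45 = 3240. Cell B exists when this is below 1.5x ULN.

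- Woman, 75 y, 50 kg: 65 × 50 × 0.85 / 3240 = 0.85 mg/dL, or 0.78–0.85x ULN. At 0.9 mg/dL her CrCl is 42.6. At 1.5x ULN (1.50–1.65 mg/dL) it is 25.6–23.3, so she is admissible down to that level.
- Man, 80 y, 55 kg: 60 × 55 / 3240 = 1.02 mg/dL, or 0.78–0.85x ULN. At 1.5x ULN (1.80–1.95 mg/dL) his CrCl is 25.5–23.5.
- 65 y, 70 kg: woman 75 × 70 × 0.85 / 3240 = 1.38 mg/dL (1.25–1.38x ULN); man 75 × 70 / 3240 = 1.62 mg/dL (1.25–1.35x ULN). CrCl at 1.5x ULN is 41.3–37.6 and 40.5–37.4.
- 55 y, 80 kg: woman 85 × 80 × 0.85 / 3240 = 1.78 mg/dL (1.62–1.78x ULN); man 85 × 80 / 3240 = 2.10 mg/dL (1.61–1.75x ULN). Both exceed 1.5x ULN, so cell B is empty.

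The conflict therefore concerns mainly older, lighter patients, some of whom have creatinine within the assumed normal range. Section 5.2 sets no upper age limit.

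**The case against.** **The conjunction may be deliberate.** Amendment 1 revised the renal criteria and cites the absence of demonstrated nephrotoxicity; Amendment 5 returned to the criterion to name the Cockcroft-Gault formula. A permissive rule requiring both abnormalities fits that history. This stands as a reason to ask the sponsor about intent. It does not remove the mismatch, because Table 5 still withholds drug on clearance alone.

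**Table 5 is about toxicity on treatment, not entry values.** Section 6.2.1 does frame dose changes around toxicity. But the clearance row asks for no change from baseline, applies whatever the grade, and lacks the baseline release given to creatinine Grade 2 in the next row. A stable low value meets it at the first chemistry check.

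**Safeguards exist.** Exclusion 4 is available, and Table 7 schedules predose chemistry on Cycle 1 Day 1 (Section 7.1 lets screening values from the preceding 3 days serve), so the hold can act at or before the first dose. This stands and limits the harm; it leaves the two rules in conflict.

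**A reader might infer that the wording is ambiguous and that sites are screening differently.** Exclusion 10 uses *and* to join separate exclusions ("known strong inducers or inhibitors of CYP3A4 and medications which increase serum phosphorus and/or calcium concentration are excluded"), and the transaminase bullet arguably does the same ("AST/SGOT and ALT/SGPT > 2.5x ULN"). But the renal bullet is grammatically clear that both limits are needed, and nothing in the documents shows a site reading it otherwise.

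**A reader might also infer an effect on the response rate.** Section 10.8.1 plans on "With at least 106 patients with FGFR2 gene fusions or translocations", so one such patient would carry 1/106 = 0.9 percentage points. That weight applies only if the patient is dosed before being held: the Full Analysis Set requires at least one dose, so a patient held beforehand carries none. The documents give no basis for claiming bias.

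**Conclusion.** The point holds as a mismatch between eligibility and dose-hold rules: exclusion 13 as written admits clearance below 45 mL/min when creatinine is at or below 1.5x ULN, and Table 5 then requires a hold with no baseline release. That conclusion rests on the protocol text alone. The examples showing that the combination is realistic rest on the assumed formula coefficients, ULNs, ages and weights; how often it occurs is unknown.

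This is a minor but worthwhile correction. Table 5 errs on the protective side, so the documents do not support reading this as planned continued dosing below 45 mL/min. Nor do they show that creatinine above 1.5x ULN must become an exclusion by itself. No response-rate, sample-size or error-rate figure changes.

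**What to change.** Make calculated (Cockcroft-Gault) or measured creatinine clearance below 45 mL/min exclusionary on its own in exclusion 13, and leave the Table 5 clearance hold as it is. In the table under working, only cell B moves, from eligible to excluded. The sponsor should confirm intent and state how the Table 5 creatinine rows apply to patients who enter with raised creatinine and adequate clearance.

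The sponsor may also keep creatinine above 1.5x ULN as a separate exclusion, that is, replace *and* with *or*. This is optional: it is not needed to resolve the clearance conflict, and it would exclude cell C as well. On the same assumptions, a 55-year-old, 80 kg patient at 1.5x ULN has a clearance of about 48.7–53.5 mL/min (woman) or 48.4–52.5 mL/min (man), so similar patients just above that creatinine would be lost. It would also leave a small boundary difference, since exclusion 13 uses above 1.5x ULN and Table 5 starts at 1.5x ULN.

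The cost is one line in an amendment and slightly narrower eligibility, mainly among older, lighter patients. The gain is that nobody is enrolled below the clearance at which the protocol withholds drug, and that screening follows the same clearance limit as dosing.

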- Section 4.2; Section 10: Revised to specify two formal interim analyses planned for Cohort 1. A Sensitivity Analysis Set for Cohort 1 was also defined (Section 10).
- Section 5.3: Removed exclusion criteria 12, 13, and 14.
- Section 5.3: Specified more precise criterion for patients with Gilbert syndrome and specified use of Cockcroft-Gault formula.
- Section 5.3: Exclusion criterion 14 (formerly 17) was made more precise.
- Section 5.3: Exclusion criterion 17 (formerly 20) was revised to cite the Clinical Trials Facilitation Group 2014 guideline and for consistency with other BGJ398 protocols.
- Section 5.3: Added exclusion criterion 20.
- Section 6 and 6.1: Specified "hard gelatin capsules" for BGJ398 oral administration. Updated and clarified instructions for BGJ398 administration.
- Section 6.2.1; Section 6.2.2; Section 6.2.3; Section 6.3.1; Section 6.3.2: Clarified dose modifications and delays, consistent with other BGJ398 protocols, including changes and additions to Table 5 (primarily for serum creatinine, blood bilirubin, hypophosphatemia, and hyperphosphatemia) and management of those and other potential study drug effects (primarily in Section 6.3.1) and of permitted concomitant therapy (Section 6.3.2).
- Section 6.3.3; Section 14.1 (Appendix 1); Section 14.2 (Appendix 2): Removed medications with a known risk of QT/QTc interval prolongation or torsade de pointes from prohibited concomitant therapy (Section 6.3.3 and Appendix 14.2). These medications were included in Table 15, Drugs to be used with caution while on study (Appendix 14.1). This change was made because preliminary PK-QTc analysis of BGJ398 did not show a relationship between drug concentration and QTc prolongation.

• Section 7.1; Section 7.2: Clarified screening and visit windows and in-clinic study drug administration. Added footnote (Table 7) to clarify FGFR2 gene fusion or translocation requirements. Removed provision for replacement of patients in Cohorts 2 and 3 for PK sampling purposes. Clarified molecular pre-screening procedures, as well as imaging requirements and guidelines. Clarified ophthalmic assessments. Added that retinal OCT can images may be collected centrally. Clarified circumstances for study treatment discontinuation. Added detail for extensive PK sampling (Table 11). Added detail for assessment of biomarkers.

Confidential

- Section 8.1.1: Removed inconsistent sentence regarding AE reporting.

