## 2.3 Rationale for dose and regimen selection

Patients enrolled in all cohorts of this study will receive 125 mg qd of BGJ398 on a 3 week on (21 day) /1 week off (7 day) schedule in 28-day cycles. This dose level and regimen is based on experiences from the CBGJ398X2101 trial.

The MTD/RP2D from the CBGJ398X2101 study was identified as 125 mg administered once daily (qd) in continuous 28-day cycles. While dose levels of 100 mg qd and higher were tolerated by patients, the majority of the patients experienced reversible hyperphosphatemia, which led to study drug interruptions. An evaluation of the drug administration records for patients prior to receiving prophylactic phosphate-lowering therapy, indicated that the median time until first dose interruption was approximately 23 days and the median duration of interruption was 7 days. This observation led to the introduction of an expansion arm in the ongoing CBGJ398X2101 study to evaluate the administration of 125 mg qd on a 3 week on (21 days) / 1 week off (7 days) schedule in 28-day cycles. To date, the majority of patients enrolled in this arm have completed their first cycle of therapy without hyperphosphatemia induced dose interruptions, while maintaining anti-tumor activity.

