  - Unstable angina pectoris or acute myocardial infarction ≤ 3 months prior to starting study drug
  - QTcF > 470 msec (males and females)
  - History of congenital long QT syndrome
- 16. Pregnant or nursing (lactating) women, where pregnancy is defined as the state of a female after conception and until the termination of gestation, confirmed by a positive hCG laboratory test
- 17. Women of child-bearing potential (WOCBP), defined as all women physiologically capable of becoming pregnant, unless they are using barrier contraception and a second form of highly effective contraception during dosing and for 3 months following the discontinuation of study treatment.

WOCBP and males whose sexual partners are WOCBP must agree to use barrier contraception and a second form of highly effective contraception (Clinical Trials Facilitation Group 2014; see Appendix 5 [Section 14.5]) while receiving study drug and for 3 months following their last dose of study drug. Alternatively, total abstinence is also considered a highly effective contraception method when this is in

line with the preferred and usual lifestyle of the patient. Periodic abstinence (eg, calendar, ovulation, symptothermal, post-ovulation methods) and withdrawal are not acceptable methods of contraception.

A woman is not of child-bearing potential if she has undergone surgical sterilization (total hysterectomy, or bilateral tubal ligation or bilateral oophorectomy at least 6 weeks before taking study drug) or if she is postmenopausal and has had no menstrual bleeding of any kind including menstrual period, irregular bleeding, spotting, etc., for at least 12 months, with an appropriate clinical profile, and there is no other cause of amenorrhea (eg, hormonal therapy, prior chemotherapy).

- 18. Sexually active males unless they use a condom during intercourse while taking drug and for 3 months after the last dose of the study drug and should not father a child in this period. A condom is required to be used also by vasectomized men as well as during intercourse with a male partner in order to prevent delivery of the drug via seminal fluid.
- 19. Have amylase or lipase  $> 2.0 \times ULN$ .
- 20. Have any known hypersensitivity to calcium-lowering agents, infigratinib, or their excipients.

## 6.1.1 Additional exclusion criteria for Cohort 3

21. Known existence of a V564F mutation in the FGFR2 gene.

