# 6.1.2 Ancillary treatments

Phosphate-lowering treatment, including low phosphate diet and phosphate binding therapy such as sevelamer hydrochloride, should be implemented prophylactically with meals on the first day of study drug initiation and modified as clinically indicated throughout BGJ398 administration. Recommendations for treatment are provided in Table 5, but should be modified as per country or institutional guidelines.

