Serum phosphorus <1.0 mg/dL (<0.3 mmol/L) (life threatening consequences)	Discontinue patient from study drug.
Hyperphosphatemia	
Serum phosphorus > 5.5 – 7.5 mg/dL	Maintain dose level of BGJ398 and optimize phosphate lowering therapy as clinically indicated
Serum phosphorus > 7.5 mg/dL for more than 7 days despite maximal phosphate-lowering therapy Or , Single serum phosphorus > 9.0 mg/dL regardless of duration or dose of phosphate lowering therapy.  (Optimize/maximize dose and schedule of phosphate lowering therapy in accordance with package insert, country or institutional guidelines.)	Hold BGJ398 dose until resolved to serum phosphorus $\leq$ 5.5 mg/dL:Restart BGJ398 at the same dose level with maximal phosphate binder dosing if the patient did not receive maximal phosphate binder dosing for serum phosphorus $>$ 7.0 mg/dL for $>$ 7 days.
	Reduce one dose level of BGJ398 if the patient had received maximal phosphate lowering therapy for serum phosphorus > 7.5 mg/dL for > 7 days or if patient had a one-time serum phosphorus of > 9.0 mg/dL. Restart BGJ398 with maximal phosphate binder dosing.
	It is recommended that phosphate binder dosing continues during BGJ398 dose interruptions for hyperphosphatemia and that serum phosphorus values be monitored frequently, e.g. every 2-3 days.
	Phosphate binder dosing should be held during the week off BGJ398 therapy each cycle (Days 22-28) and during BGJ398 dose interruptions for nonhyperphosphatemia adverse events.
Serum phosphorus with life-threatening consequences; urgent intervention indicated (e.g., dialysis)	Discontinue patient from study drug
Hypercalcemia	
Serum calcium Grade 2	
 
Hold BGJ398 dose until resolved to Grade 1 or baseline:
 
if resolved within ≤ 7 days after suspending BGJ398, maintain dose level.
 

Worst Toxicity CTCAE v4.03 Grade (unless otherwise specified)	Dose Modifications any time during a cycle of therapy
	
 
if resolved between > 7 days and 14 days after suspending BGJ398, ↓ 1 dose level.
 
if not resolved within ≤14 days, discontinue patient from study treatment.
 

Serum calcium Grade ≥3	Discontinue patient from the study treatment
Nervous system disorders	
Neurotoxicity	
Grade 2	Omit dose of BGJ398 until resolved to CTCAE Grade ≤ 1, then ↓ 1 dose level of BGJ398. If not resolved within ≤14 days, discontinue patient from study drug.
Grade $\geq 3$	Discontinue patient from study drug treatment
GI disorders	
Pancreatitis	

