# Management of Hyperphosphatemia

Hyperphosphatemia is a recognized on-target effect of potent and selective inhibitors of the FGFR pathway. While on BGJ398, patients should avoid foods that are especially high in phosphate and, if possible, should restrict dietary phosphate to 600 – 800 mg/day. High-phosphate foods include dairy products; meats, nuts, and other high-protein foods; processed foods; and dark colas.

Patients who have experienced hyperphosphatemia should take a phosphate binder such as sevelamer, sucroferric oxyhydroxide, lanthanum carbonate, ferric citrate, etc. within 30 minutes of a meal on the day while taking BGJ398. Once the patient has had hyperphosphatemia, the patient should remain on a low phosphate diet, if possible, and take phosphate binder on the days BGJ398 is taken, even if the serum phosphorus is normalized. Unless otherwise specified by the local package insert or institutional practice, the following regimen should be used to manage hyperphosphatemia:

- For serum phosphorus > 5.5 7.5 mg/dL
  - Start sevelamer 800 mg three times a day with meals
  - Increase the dose of sevelamer up to 1200 mg every 8 hours
- For serum phosphorus ≥7.5 mg/dL
  - o Increase the dose of sevelamer up to 1600 mg (2 tablets per meal) every 8 hours
  - Consider adding acetazolamide two to three 250 mg tablets per day.

During the BGJ398 cycle, patients do not need to be on a low phosphate diet or take a phosphate binder during their 1-week off period unless serum phosphorus is not normalized. Other dose modifications are provided in Table 5, but should be modified as per country or institutional practice.

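### Exclusion criterion 20 screens for hypersensitivity to calcium-lowering agents, which the protocol never prescribes, and omits the phosphate-lowering agents that should start on Day 1; the practical effect is small

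*Protocol*

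**What the plan says.** Exclusion criterion 20 (Protocol Section 5.3) applies to all cohorts and bars patients who "Have any known hypersensitivity to calcium-lowering agents, infigratinib, or their excipients". The Amendment 5 change list records it only as "Section 5.3: Added exclusion criterion 20", with no reason for the wording.

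On ancillary treatment, Section 6.1.2 says that "phosphate binding therapy such as sevelamer hydrochloride, should be implemented prophylactically with meals on the first day of study drug initiation". Section 6.3.1 adds that patients who have had hyperphosphatemia "should take a phosphate binder such as sevelamer, sucroferric oxyhydroxide, lanthanum carbonate, ferric citrate, etc", with doses stepped up by phosphorus level. After a hold for hyperphosphatemia, Table 5 gives two routes back to treatment, and both call for maximal binder dosing. The dose-reduction route ends: "Restart BGJ398 with maximal phosphate binder dosing".

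For hypercalcemia, the Grade 2 row of Table 5 reads "Hold BGJ398 dose until resolved to Grade 1 or baseline", followed by rules on resuming, reducing or stopping according to time to resolution. Grade 3 or higher means discontinuation. No drug to lower calcium is named in either row.

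**The concern.** A hypersensitivity exclusion normally covers the study drug and whatever else the protocol expects patients to take. Criterion 20 covers the study drug, but the ancillary class it names does not match the regimen. Two consequences follow.

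- **Omission.** Nothing in the eligibility criteria prompts a site to ask about intolerance of the drug class that should start with the first dose. A patient who could take no binder at all could be enrolled and could not then follow the written restart rule after a phosphate-related hold.
- **Over-exclusion.** A patient hypersensitive to a calcium-lowering drug must be excluded, although no section directs its use. Section 5.1 requires that patients offered treatment meet none of the exclusion criteria, and Section 12 allows no authorised deviations, so a site cannot waive the criterion.

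Binder use is likely to be common. Section 2.3 reports that, at 100 mg daily and above in the phase I study, "the majority of the patients experienced reversible hyperphosphatemia, which led to study drug interruptions".

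**Working it through.** The documents give no figure to reproduce on this point. The check compares sections and then bounds the number of patients affected.

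**Comparison of sections**

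| Class | Where the protocol uses it | In criterion 20? |
|---|---|---|
| Phosphate-lowering | Section 6.1.2 (prophylaxis with the first dose); Table 5 (both restart routes); Section 6.3.1 (titration); SAP Sections 2.7.2.1.2 and 5.11 (planned summary and drug list) | No |
| Calcium-lowering | Not directed anywhere. Table 5 hypercalcemia rows give BGJ398 dose actions only. Section 6.3.1 permits bisphosphonates, but as care for bone metastases. | Yes |
| Infigratinib | Study drug | Yes |

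The other exclusion criteria in Section 5.3 do not name phosphate-lowering agents. The nearest is criterion 4, which leaves other medical conditions to the investigator's judgment.

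**How many patients could be screened under criterion 20**

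1. The first formal Cohort 1 interim analysis is reported in the past tense in Amendment 5 (Sections 4.2 and 10.7), so its patients were enrolled before the criterion existed.
2. Its efficacy set held 72 patients with FGFR2 fusions or translocations (Section 10.8.1). It also took in everyone enrolled before Amendment 2 (Section 10.1.2), and so the 14 patients with other alterations (Section 2.2). Already enrolled: at least 72 + 14 = 86.
3. Planned total: up to about 160 (Section 4.1). Enrolled under criterion 20: at most 160 - 86 = 74.
4. If Cohort 1 was already complete, only Cohorts 2 and 3 remain: about 20 + 20 = 40. If Cohort 3 also stops at 10 (Section 10.8.2): 20 + 10 = 30.

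**Expected number with binder hypersensitivity**

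The prevalence is an assumption of 0.5% to 1%. Expected number = patients × prevalence.

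| Patients | At 0.5% | At 1% |
|---|---|---|
| 74 (ceiling) | 74 × 0.005 = 0.37 | 74 × 0.01 = 0.74 |
| 40 (Cohorts 2 and 3) | 40 × 0.005 = 0.20 | 40 × 0.01 = 0.40 |
| 30 (Cohort 3 stops early) | 30 × 0.005 = 0.15 | 30 × 0.01 = 0.30 |

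Every scenario gives less than one patient. These counts are patients with the hypersensitivity, not patients harmed by it; the latter would be fewer.

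**The case against.** The strongest reply is that the rest of the protocol already handles this.

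- **Alternatives and local practice.** Section 6.3.1 lists several binders, a low-phosphate diet and acetazolamide, and defers to the local package insert or institutional practice. Table 5 likewise defers to package inserts and guidelines. Section 6.1.2 is worded as a recommendation. A single phosphorus value above 9.0 mg/dL triggers a hold whatever the binder dose, and criterion 4 leaves room for judgment. All of this stands, and it is why the effect is small. None of it brings criterion 20 into line with the regimen, and criterion 4 cannot reverse an exclusion made under criterion 20.
- **Calcium-lowering may have been meant.** Section 6.2.3 sends treatment that the protocol does not specify to local guidelines, so a site might treat hypercalcemia with a drug of its own choosing. Hypercalcemia is also part of an adverse event of special interest in the SAP. This is a fair point: the intent is not known, and a drafting slip is an inference. The phosphate omission remains under either reading.
- **Section 2.3 needs its context.** The interruptions it describes arose under continuous dosing, and the interruption timing came from records before prophylactic phosphate-lowering therapy. On the three-weeks-on, one-week-off schedule used here, most patients completed their first cycle without such interruptions. That weakens Section 2.3 as evidence on how often doses will be interrupted in this trial. Expected binder use still follows from Section 6.1.2.

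**Conclusion.** The criterion is wrong as written: the ancillary class it names is not one the protocol prescribes, and the class the regimen depends on is absent. The mismatch is certain from the text; the reason for it is not.

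The consequence is minor. At most 0.37 to 0.74 patients with binder hypersensitivity would be expected, resting on an assumed 0.5-1% prevalence and on the ceiling of 74 later enrolments. Alternative binders reduce the number who would be disadvantaged. The number wrongly excluded over calcium-lowering agents cannot be sized from the documents. Response rate, analysis sets, sample size and the Cohort 3 expansion rule are unaffected. This is a small patient-safety and eligibility correction, desirable rather than essential.

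**What to change.** Reword criterion 20 to exclude known hypersensitivity to phosphate-lowering agents, to infigratinib, or to the excipients of either. Keep calcium-lowering agents in the list only if the sponsor confirms that class was intended, and in that case state where it would be used. Add that a patient intolerant of one binder may enrol if a suitable alternative can be given, so that the change does not restrict recruitment in a rare disease.

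The cost is one sentence at the next protocol amendment, with no new data, procedures or analyses.
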